Gender disparities faced by Appalachian women call for the critical need for prevention services for this high-risk population. Research indicates that women drug users, in general, are more likely to have injecting intimate partners, and with fewer economic resources to buy drugs, they are more likely to engage in sex exchange to obtain drugs. Studies of rural women drug users are challenging because recruitment of this high-risk population can be limited by the lack of formal treatment opportunities, travel distances to study sites, and the general protective nature of rural social networks (Friedman, 2003). This study will utilize local rural jails as venues for screening and recruitment of high-risk women drug users, followed by targeted prevention efforts in the community post-release. Eligibility criteria for this study includes: 1) NM-ASSIST indicators of high-risk drug use during the 6 months before jail (including injection); 2) engagement in at least one sexual risk behavior in the past 3 months; 3) no evidence of cognitive impairment (GAIN, Dennis, 1998), 4) no evidence of active psychosis (currently experiencing hallucinations), 5) no self-reported current symptoms of physical withdrawal from a recent episode of drug use; 6) self-reported HIV negative status; 7) projected jail release date within 3 months; 8) active Facebook user prior to entering jail (defined as having a Facebook account that was checked at least once a week); and 9) reside in a rural, Appalachian county prior to incarceration. This R34 pilot study proposes to enroll 20 rural women and 10 stakeholders in the focus group phase (n=30) and 60 rural women from the two proposed jail sites during the pilot phase. It is expected that participants who meet eligibility criteria and enter the study will be about 33 years old, mostly white (98%, reflecting the central Appalachian region), about a quarter will be single (24%), and have a high school diploma or GED (27%). The majority will report a history of poly-drug use including prescription opioid misuse, marijuana, and cocaine. Dates of study enrollment are projected to be 4/1/18 - 3/31/21.

Attachments

Indicate the targeted/planned enrollment of the following members of minority groups and their subpopulations. Possible demographic sources: [Census Regional Analyst Edition](#), [Kentucky Race/Ethnic Table](#), [Kentucky Population Data](#).

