Based on our current study, we anticipate that most of our participants will be on probation rather than parole. However, confidentiality issues will be stressed during informed consent and will include the description of a federal Certificate of Confidentiality. Participants will also be assured that their screening results, HIV/HCV test results, study participation, and study data will not be made available to any representative of the jail or criminal justice system. Jail officials and administrators will not be informed of participants who participate in the screening, eligibility data, or refusals in order to protect participant confidentiality. Consent form language reflects this emphasis on participant confidentiality.

Condition 5. For studies that require follow-up, provisions are made including consideration for the length of individual sentences; informed consent must reflect provisions for follow-up.

Describe what provisions have been made for follow-up and how this information will be relayed to the prisoner participants:

For this pilot study, follow-up data will be collected 3 months post-release from jail to assess feasibility and acceptability of the FB intervention, as well as self-report measures at 3 months to assess ratings of acceptability and feedback. In addition, measures are proposed for field testing during the 3 month follow-up to examine relevant covariates and participant characteristics which may influence intervention behavioral outcomes, as well as to examine integrity of our randomization procedures. To achieve a high follow-up rate, participants will also be asked to provide telephone numbers of the person who is most likely to know where they will be when they are released (usually a mother or grandmother). Locator information will also include Facebook, primary and secondary addresses, telephone numbers, hangouts, aliases, and contact information for close relatives, and friends. Once located, follow-up interviews will be face-to-face and will be conducted at a location mutually agreed upon by participants and the study coordinator. Participants will be informed about follow-up interviews and time intervals at the baseline interview, and they will be provided with incentives for completed interviews.

Condition 6. Information about the study is presented in a language understandable to prisoners.

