Potential participants who are interested in the study will be asked to participate in the screening session at the jail with the UK research coordinator. Potential participants will be provided with informed consent prior to the collection of screener data. As part of the informed consent process, potential participants will be assured that: (a) Neither participation nor refusal to participate in a protocol will affect their legal parole status (if applicable); (b) No individual or identifiable data collected as part of a study protocol will be made available to any criminal justice authority including jail, parole, or community mandated treatment; and (c) If potential participants do NOT wish to participate, their parole or other legal status will not be affected. Potential participants who choose NOT to participate in the study protocol will not be identified in their records, and non-participation will NOT become a matter of official record in any file. For the focus groups, the consent procedure will only cover the focus group. For the pilot trial, informed consent procedures will cover participation in the screener, baseline interview, HIV/HCV testing, intervention participation, and follow-up interviews so that participants are fully aware of all possible study procedures before making a decision about entering the study. Due to the sensitive nature of some of the questions asked in the interviews, confidentiality issues will be stressed during informed consent which will include a description of a federal Certificate of Confidentiality which provides an additional layer of human subject protection. Participants will also be assured that their screening results, study participation, and study data will not be made available to any representative of the criminal justice system. The research coordinator will keep detailed records on the number of interested participants who participate in the screening session and the number of refusals. Screening data will be examined as part of the implementation phase to examine characteristics of participants who enter the study compared to those who are not eligible. Because of the short time frame between baseline and follow-up interview (3 months), consent procedures will not be repeated since no new procedures will be introduced.

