The Kentucky Department of Corrections (DOC) requires us to provide the DOC with the study title and participant name of individuals under their supervision, including inmates, parolees, or individuals likely to be incarcerated by the DOC. This information is sent to: [name], Director of the Office of Research and Legislative Services for the Kentucky Department of Corrections.

**Due to COVID-19 restrictions in the jails, we are requesting a waiver of documented informed consent (described in detail in the Informed Consent page). Research staff will still review the consent in detail with potential participants and there will be a section added to the IRB-approved consent document for staff to verify that they reviewed the consent with the participant, answered any questions, that the participant agreed to participate in the study, and the participant's name. Once COVID-19 restrictions are lifted the previously approved process of documented informed consent will resume.

Participants will be encouraged to call the Principal Investigator if any questions arise during the course of the research. Phone numbers for the PI and the ORI are included in the consent form. It is expected that providing the phone number and contact information for the PI may offer a safe, confidential, and reliable channel for participants to express problems, concerns or questions, and obtain study information since the PI will not, on most occasions, be the person originally collecting the data.

Request for Waiver of Informed Consent Process

If you are requesting IRB approval to waive the requirement for the informed consent process, or to alter some or all of the elements of informed consent, complete, Section 1 and Section 2 below.

Note: The IRB does not approve waiver or alteration of the consent process for greater than minimal risk research, except for planned emergency/acute care research as provided under FDA regulations. Contact ORI for regulations that apply to single emergency use waiver or acute care research waiver [contact]).

SECTION 1.

Check the appropriate item:

I am requesting a waiver of the requirement for the informed consent process.

I am requesting an alteration of the informed consent process.

If you checked the box for this item, describe which elements of consent will be altered and/or omitted, and justify the alteration.

SECTION 2.

Explain how each condition applies to your research.

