All research data will be kept in locked file cabinets in the office of the Principal Investigator at the University Of Kentucky Department of Behavioral Science ([name]). Each participant will receive a unique identifying number. All research data collection instruments will be identified by this number only. The master list matching identifiers to specific participants will be maintained in a locked file in the PI's office. Research data will be reported in aggregate form only. Computer files will be retained and all electronic data will be password protected, stored on secure UK-maintained servers, and accessible only by the researchers on this study. In addition, no DOC personnel (including jail staff or personnel, probation/parole officers, etc) will be asked about participants information for locating and tracking for follow-up. The consent form includes a statement about access to state-maintained records including the KOMS system (Kentucky Offender Management System) which is standard for offender protocols at UK CDAR. Information on participants in the study should be available from those systems and through self-reported locator information.

All interviews will take place in private, confidential office setting in the jail setting. All data collected will be kept in password protected files on a secure server and under lock/key. Clients will also be reminded that their legal status will not be altered based on their participation in the study. As an additional safeguard to ensure protection of client confidentiality, a Certificate of Confidentiality will be obtained from DHHS.

UK IRB policies state that IRB-related research records must be retained for a minimum of 6 years after study closure. Do you confirm that you will retain all IRB-related records for a minimum of 6 years after study closure?

Yes No

Payment

Describe the incentives (monetary or other) being offered to subjects for their participation. If monetary compensation is offered, indicate the amount and describe the terms and schedule of payment. Please review [this guidance](#) for more information on payments to subjects, including restrictions and expectations.

Focus group participants (n=30) in phase 1 will receive \$10 for attending the one-time one-hour focus group. Participants in the pilot trial will receive \$25 for taking part in the research interviews for study at baseline and at follow-up (3-months post release).

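### Women are assured that the criminal justice system will not learn they joined the study, yet the plan sends covered women's names and the study title to the Department of Corrections

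*Combined protocol and SAP*

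**What the plan says.** The combined protocol and SAP gives the assurance twice.

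- Prisoners, Section 2, Condition 4 (parole boards): screening and test results are covered, and "study participation, and study data will not be made available to any representative of the jail or criminal justice system".
- Informed Consent Process: women will be assured that "their screening results, study participation, and study data will not be made available to any representative of the criminal justice system". Item (b) of the same paragraph adds that no individual or identifiable data collected under the protocol will go to a criminal justice authority.

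The next paragraph of the Informed Consent Process response describes the report. The DOC "requires us to provide the DOC with the study title and participant name of individuals under their supervision, including inmates, parolees", and also of people likely to be incarcerated by it. The text then names a DOC director's office as the recipient.

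Two features of the consent process bear on this. The focus groups have their own consent: "For the focus groups, the consent procedure will only cover the focus group". For the pilot trial, given the short interval to follow-up, "consent procedures will not be repeated since no new procedures will be introduced".

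A Certificate of Confidentiality is planned (Condition 4, Informed Consent Process, and Records, Privacy, and Confidentiality). Prisoners, Section 5 says that legal counsel should be contacted where a study involves such a certificate.

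**The concern.** The assurance covers the fact of taking part as well as the answers given. A list of names under a study title discloses exactly that fact. Under Project Information the full title refers to HIV prevention and to rural women drug users, so the list also suggests why a woman was eligible.

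Pilot participants are in jail when they enrol (Prisoners, Section 1). Who will learn of her participation is something a jailed woman may reasonably weigh before agreeing. The Condition 4 answer is also one of the six justifications that the IRB must find and document for prisoner research, so the IRB is relying on a statement that another part of the application does not let the study keep. Because pilot consent is not taken again at follow-up, a wrong assurance at enrolment is not corrected later.

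**Working it through.** No formula applies to the contradiction. The check is to set the texts side by side, look for a reconciling statement, and bound the number of women affected.

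**Step 1: do the two statements concern the same thing?**

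| | Assurance | Report |
|---|---|---|
| Where | Condition 4; Informed Consent Process | Informed Consent Process, next paragraph |
| Item | Participation, results and data | Name and study title |
| Recipient | No representative of the criminal justice system | A DOC director's office |
| People | All participants | Those under DOC supervision or likely to be incarcerated by it |

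Name plus title discloses participation, and the DOC is part of the criminal justice system. The two statements cannot both hold for a covered woman.

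**Step 2: is there an exception elsewhere?** None is stated. Other confidentiality text is equally unqualified. Records, Privacy, and Confidentiality says no data go to jail or other criminal justice officials. Item (5) under Data and Safety Monitoring restricts review of identifying data to study staff. Whether these two statements and item (b) are also contradicted depends on whether a reported name counts as data, so they need reconciling but are not the main conflict. The risk text (Condition 2, and Potential Risks & Benefits) describes a possible breach of confidentiality, not a planned disclosure.

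**Step 3: what is not contradicted?** The report carries only names and the title. The assurances on screening results, HIV/HCV results and interview answers stand. So do items (a) and (c) of the consent paragraph, that joining or refusing will not affect parole or other legal status.

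**Step 4: how many women?** Study Population plans "20 rural women and 10 stakeholders in the focus group phase (n=30) and 60 rural women from the two proposed jail sites". The 10 stakeholders are service providers and are not counted.

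- Pilot women, all incarcerated at enrolment: 60.
- Focus-group women, if recruited in jail, as Subject Recruitment Methods & Advertising implies: 20.
- Ceiling: 60 + 20 = 80.

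The documents do not say who counts as under DOC supervision, so they give no lower bound. Project Information's maximum of 193 subjects is not broken down by phase and is not used.

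**The case against.** The strongest reply is that the report paragraph is itself the exception: a specific DOC rule placed directly after a general assurance, in the box that describes consent. That softens the conflict. But the paragraph is not worded as a qualification and does not say women are told, and Condition 4 repeats the assurance with no such paragraph nearby.

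A second reply is that staff work from the consent form, which is not available here and may disclose the report. Prisoners, Section 5 mentions a DOC-approved research consent, and Records, Privacy, and Confidentiality says the form already covers access to state offender records. This stands as a limit. A reader might infer that women are misled or never told; the documents do not support that, because the forms cannot be seen. It does not remove the conflict. If the form discloses the report, staff giving the assurance would contradict the form; if it does not, women hear only the assurance.

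A reader might also infer that most participants would be named. Condition 4 says "we anticipate that most of our participants will be on probation rather than parole", and a confidentiality paragraph says "no DOC personnel (including jail staff or personnel, probation/parole officers, etc) will be asked about participants information", which seems to place probation officers within the DOC. The inference fails. The first statement answers a question on parole boards and compares two statuses, and the report paragraph does not name probationers. The second also lists jail staff as DOC personnel, so read literally it would point to every jailed woman. It cannot settle who is under DOC supervision. Nor does the mention of inmates show that all 60 pilot women are covered, since nothing says whether women held in these two jails are under DOC supervision.

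**Conclusion.** The point holds as an internal contradiction in the consent text. For any woman covered by the DOC report, the assurance that her participation is kept from the criminal justice system is untrue as written. The number covered is not stated and cannot be derived; at planned enrolment it is at most 80, which includes the 20 focus-group women only if they are recruited in jail.

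The conclusion rests on the plan text alone. It assumes only that a name sent with a study title reveals participation. It does not extend to test, screening or interview data or to the parole assurances, and it makes no claim about what women are actually told. Endpoints, sample size and analysis are unaffected. It should still be corrected, because the assurance concerns incarcerated women and a sensitive title.

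**What to change.** 1. Ask legal counsel, as Prisoners, Section 5 directs for studies with a Certificate of Confidentiality, whether the name-and-title report must be made. The documents do not settle this, and it should be known before the assurance is narrowed.
2. If the report must be made, replace the unqualified assurance on participation in Condition 4 and the Informed Consent Process. State that the DOC receives the name and study title of covered women, but no screening, HIV/HCV test or interview data. Name this planned disclosure in the risk text under Condition 2 and Potential Risks & Benefits.
3. If it need not be made, remove the report from the Informed Consent Process and keep the assurance.
4. Either way, bring item (b) of the consent paragraph, the statement under Records, Privacy, and Confidentiality, and item (5) under Data and Safety Monitoring into line. Make the pilot consent form, the focus-group consent and the verbal consent review used during COVID-19 restrictions say the same thing.
5. Because consent is not repeated, ask the IRB whether women already enrolled should be told. Enrolment was projected to end on 3/31/21, so this may be the most pressing part in practice.

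The cost is a legal query and an IRB amendment to protocol wording, and to consent wording where the forms do not already agree. Some women may decline once told of the report; the documents give no figure for this. No outcome, analysis or sample size changes.

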Consistent with strategies used in the current R01 trial (IRB protocol #12-0372), participant recruitment for the pilot study in each of the rural jails (Leslie County Detention Center and Kentucky River Regional Jail) will occur once a month based on a randomized schedule involving days of the week and times of the day. On each recruitment day, a targeted number of women offenders serving time in the jail will be randomly sampled from the daily census sheet. All women residing in the jail on the day of screening will have an equal opportunity of being selected, including minorities, as long as they are at least 18 years of age and not previously screened for the study. Following random selection, participants will be screened to identify rural women who have engaged in high risk drug use and HIV risk behaviors, and who are regular Facebook users. Eligibility criteria for this pilot study includes: 1) NM-ASSIST indicators of high-risk drug use during the 6 months before jail (including injection); 2) engagement in at least one sexual risk behavior in the past 3 months; 3) no evidence of cognitive impairment (GAIN, Dennis, 1998), 4) no evidence of active psychosis (currently experiencing hallucinations), 5) no self-reported current symptoms of physical withdrawal from a recent episode of drug use; 6) self-reported HIV negative status; 7) projected jail release date within 3 months; 8) active Facebook user prior to entering jail (defined as having a Facebook account that was checked at least once a week); and 9) reside in a rural, Appalachian county prior to incarceration.

b) Describe what measures will be taken to prevent intervention by prison authorities in the selection process:

Consistent with our current R01 (IRB protocol #12-0372), while jail staff may monitor participant entry and exit into the visitation room for the screening and interview process, no jail staff will be present for the screening administration and confidential baseline interviews.

Condition 4. Parole boards cannot take into consideration a prisoner's participation in research. Informed consent must state participation will not impact parole.

Describe what measures are in place to ensure parole boards are not influenced by prisoners' participation in research and how prisoners will be told their participation (or refusal or withdrawal from) will not impact parole:

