UK staff will recruit participants from each of the rural jails once a month based on a randomized schedule. On each recruitment day, UK research staff will randomly select women offenders serving time in the jail from the daily census sheet to participate in the screening sessions. Jail personnel are not involved in the random selection of cases, and they will only providing access to the daily census sheet. UK research staff will randomly select participants from all women residing in the jail on the day of screening who meet the time frame criteria of at least two weeks– three months incarcerated, and all women inmates will have an equal opportunity of being selected for inclusion in the screening process by the UK research team, including minorities, as long as they are at least 18 years of age and not previously screened for the study. Focus group recruitment will occur 1-2 times, depending on interest. Beginning in Month 13, approximately 5 women will be recruited into the pilot trial each month across both jails in order to maintain a manageable number of participants in the intervention conditions.

**During COVID-19 restrictions, we propose to change the recruitment to hang sign-up sheets (attached in the research procedures section) in the women's cells at both jails to allow women to volunteer for the study. All women who volunteer on the sign-up sheet will be contacted for screening. Once COVID-19 restrictions are lifted, study recruitment will return to previously approved methods. Advertising materials will not be used in this study.

Attachments

Research Procedures

Describe how the research will be conducted.

- What experience will study participants have?
- What will study participants be expected to do?
- How long will the study last?
- Outline the schedule and timing of study procedures.
- Provide visit-by-visit listing of all procedures that will take place.
- Identify all procedures that will be carried out with each group of participants.
- Describe deception and debrief procedures if deception is involved.

Differentiate between procedures that involve standard/routine clinical care and those that will be performed specifically for this research project. List medications that are explicitly forbidden or permitted during study participation.

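### COVID-period sign-up sheets in the cells have no stated confidentiality safeguard, sit in tension with the promises about jail officials, and change the enrolment denominator

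*Combined protocol and SAP*

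**What the plan says.** Under the standard method (Subject Recruitment Methods & Advertising), research staff draw women at random from the daily census sheet, and "Jail personnel are not involved in the random selection of cases"; the jail only gives access to that sheet.

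During COVID-19 restrictions the same section makes a temporary change: to "hang sign-up sheets (attached in the research procedures section) in the women's cells at both jails to allow women to volunteer for the study". It continues: "All women who volunteer on the sign-up sheet will be contacted for screening". Recruitment reverts to the standard method when restrictions end.

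Two promises bear on this:

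- Prisoners, Section 2, Condition 4: "Jail officials and administrators will not be informed of participants who participate in the screening, eligibility data, or refusals".
- Informed Consent Process: women are assured that "their screening results, study participation, and study data will not be made available to any representative of the criminal justice system".

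The Research Procedures section lists the sign-up sheet and a COVID-19 summary table as attachments. Neither is among the documents supplied. The Data Analysis section names the proportion of women agreeing to enrol as a feasibility indicator and expects participation of about 90% across its indicators.

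**The concern.** For a woman to be contacted, she must identify herself on or through the sheet. If the sheet is a shared list hung in a cell, her interest in the study can be seen by people whom the plan elsewhere undertakes to keep uninformed, and by cellmates. The women are incarcerated and the study concerns drug use and HIV risk, so this is a matter of participant protection.

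There is also a consequence for the data. A named feasibility indicator is the share of women who agree to enrol. Changing from sampled women to women who put themselves forward changes what that share measures. If the two groups are pooled without a record of route, the result is hard to interpret and hard to carry into the planning of the larger trial.

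**Working it through.** No figure in the plan bears on the confidentiality point, so the check is a comparison of sections.

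1. **What a signature leads to.** Every woman who volunteers on a sheet is contacted. The sheet therefore coincides with the list of women approached for screening. It is not the list of women screened, because consent precedes any screener data and a woman may still decline.

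2. **When she signs.** The Informed Consent Process section gives the confidentiality assurances and describes the Certificate of Confidentiality during consent, at the screening session. Signing the sheet comes earlier, so a woman may disclose interest before hearing those protections.

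3. **Who could see it.** The supplied text does not say what a woman writes, whether entries stay visible, or who posts and collects the sheets. Research Procedures ties the COVID-19 changes to times when research staff cannot physically meet participants. If they cannot enter, jail personnel may well handle the sheets. That is an inference; the documents do not state it.

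4. **Which promises are touched.** Condition 4 covers jail officials and administrators, and the consent assurance covers criminal justice representatives. Neither covers cellmates. Exposure to cellmates is a privacy concern and contradicts no promise in the plan.

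5. **Whether the text on fair selection was updated.** Condition 3 of the same Prisoners section asks how selection is protected from the authorities. Its answer describes census sampling and the absence of jail staff from screening and interviews. It does not mention the sheets.

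6. **The starting point.** Visibility to the authorities was already not zero. Condition 3 allows that "while jail staff may monitor participant entry and exit into the visitation room for the screening and interview process". The Informed Consent Process section also says that the study title and participants' names go to the Department of Corrections for women under its supervision. That disclosure concerns participants, not every woman who asks to be contacted.

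7. **The enrolment proportion.** Let p_c be the proportion agreeing among census-sampled women, p_v the proportion among sheet volunteers, and w the share of approached women who came from the census. The pooled figure is

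   p = w × p_c + (1 − w) × p_v.

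   The documents give none of w, p_c and p_v. The pooled figure depends on how long restrictions lasted, through w, as well as on acceptability. Volunteers have already expressed interest, so p_v may exceed p_c, but the size of any gap cannot be derived from the documents. The research coordinator is to record the numbers screened and the refusals; nothing supplied says that recruitment route is recorded.

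**The case against.** The strongest reply is that the point rests on attachments that nobody reading these documents can see. No section calls the sheets open or says that names remain on view. Tear-off slips, one form per woman, coded entries or folded returns would create no visible list. This stands, and it rules out a stronger reading that a reader might infer: that the sections contradict each other outright whatever the sheet looks like. Format and handling decide that question, and they are unconfirmed.

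Three further replies also stand:

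- A signature shows that a woman asked to be contacted, not that she was screened, eligible or enrolled.
- Jail staff could already see women going to screening, so the sheets would widen an existing gap and not break an intact guarantee.
- Nothing supplied shows that the sheet mentions drug use or HIV. The study's Facebook site carries a neutral name, Women's Health Study, and the sheet may do the same.

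A reader might also infer that women worried about disclosure will not sign, which would bias uptake. The documents offer no evidence for this. The selection change that they do establish is the move from random sampling to volunteering, and private slips would not remove it.

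What the replies do not supply is a safeguard. Existing visibility elsewhere is no reason to add a further route, and a temporary procedure still needs one for as long as it runs.

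**Conclusion.** The point holds as an unresolved tension and a cheap improvement, not as a demonstrated breach. The supplied text puts sign-up sheets in the cells, contacts everyone who uses them, and describes nothing that keeps the entries from jail staff or other inmates, while two other sections promise that officials and criminal justice representatives will not learn who is screened or takes part.

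The size cannot be computed. The number of pilot women recruited by sheet is not stated; it lies between 0 and the planned 60, and any woman who signs without enrolling adds to those exposed. The effect on uptake is likewise unknown.

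The confidentiality conclusion assumes that the sheet is a shared list that others can see. If the attached form already provides private, individual return, that part falls away, and what remains is to say so in the text. The conclusion on the enrolment proportion does not depend on the form: under any volunteer method the denominator changes from randomly sampled women to self-selected ones.

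**What to change.** - **Form.** Unless the attached form already does this, replace the sheet with individual slips returned in sealed envelopes addressed to the study and carrying only a neutral study name.
- **Handling.** State who distributes and collects the slips when research staff cannot enter the jail. Sealed envelopes suit that situation better than a box that only research staff may open, which would need them on site.
- **Consistency.** Reconcile the COVID-19 paragraph in Subject Recruitment Methods & Advertising with Conditions 3 and 4 of the Prisoners section and with the Informed Consent Process section, so that the selection procedure and the confidentiality promises describe what is actually done.
- **Analysis.** Record recruitment route (census sample or volunteer) for each woman approached. Report the proportion agreeing to enrol separately by route, and do not rely on a pooled figure alone. Private slips do not remove self-selection, so this is needed even if the form is changed.

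The cost is slips and envelopes, one added data field, a short IRB modification and slightly slower contact with volunteers.
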